3.2.2.1 Study Drug: KW-0761 (mogamulizumab)

Treatment can be administered on an outpatient basis. Subjects will receive 1.0 mg/kg of KW-0761 as an intravenous (iv) infusion over at least 1 hour on Days 1, 8, 15 and 22 of the first cycle and on Days 1 and 15 of subsequent cycles. Each treatment cycle is 28 days.

No dose modifications of the KW-0761 will be permitted in this study. Subjects will not be replaced.

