5 STUDY ASSESSMENTS

5.1 Efficacy Evaluations

Response in skin and blood will be evaluated every 4 weeks during treatment. In the first year of treatment, response in lymph nodes and viscera and the overall global composite response (including skin, blood, lymph nodes, and viscera) will be documented at 4 weeks after the start of study treatment (end of Cycle 1) and every 8 weeks thereafter (Cycle 3, 5, etc.). After the first year, response in the lymph nodes and viscera and the overall global composite response will be documented every 16 weeks (Cycle 17, 21, etc.).

For those subjects who cross over from the vorinostat arm to KW-0761 treatment, response within the second arm of the study will be measured from the first day of dosing with KW-0761. Baseline measurements for this arm are considered to be those taken at the last assessment which documented progression on vorinostat or if repeated, assessment completed closest to and before the first KW-0761 infusion (i.e., mSWAT done on Cycle 1, Day 1 is the new baseline).

Prior to starting study treatment, visual inspection of the skin with photographs and measurements Severity Weighted Assessment Tool (SWAT), assessment of CT images and hematological examinations will be done to document extent of disease. Skin disease will be evaluated using a modification of the SWAT. Response for skin will be based on modified SWAT (mSWAT) scores. In addition, pruritus will be evaluated using a Likert scale and Itchy QoL. Lymph nodes and visceral disease will be evaluated by CT. The response in blood will be assessed by flow cytometry.

The response in all compartments (skin, blood, lymph nodes and viscera, as applicable) and overall response will be assessed, except as otherwise noted, in accordance with the response criteria determined by consensus of the International Society of Cutaneous Lymphomas (ISCL), the United States Cutaneous Lymphoma Consortium (USCLC) and the Cutaneous Lymphoma Task Force of the European Organization for Research and Treatment of Cancer (EORTC) as noted in Table 5.1-1 below.³

Table 5.1-1 Global Composite Scoring System

Global Score	Definition	Skin	Nodes	Viscera	Blood
CR	Complete disappearance of all clinical evidence of disease	CR	All categories have CR/NI		
PR	Regression of measurable disease	CR	All categories do not have a CR/NI and no category has a PD		
		PR	No category has a PD and if any other category involved at baseline, at least one has a CR or PR		

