6.3 Determination of Sample Size

Since the primary endpoint is PFS, the reference median PFS for vorinostat is assumed to be 169 days.⁵ The median PFS for KW-0761 therapy is targeted for 254 days, a 50% improvement over this reference median. For a 24-month accrual and 12 month follow-up on the last subject dosed, Table 10.3-1 of the protocol gives the power and the number of PFS events required to show superior PFS for KW-0761 therapy over vorinostat at the one-sided

0.025 significance level. The Intent-to-Treat (ITT) set is used for this primary analysis. The same analysis conducted using the Efficacy Evaluable set is considered secondary.

Under these assumptions, for the ITT population, a total of 255 PFS events will give 90% power. For this study, the final primary analysis comparing PFS between treatment groups will not be conducted until 255 PFS events occur or until a maximum of 24 months after the last randomized subject's first dose, whichever comes first. In the event that the study is stopped prior to 255 PFS events being observed, the primary test will be performed at less than 90% power under the current assumptions according to Table 10.3-1 in the protocol.

Each of these calculations used a log-rank test to compare the two survival curves. Sample size calculations were computed using SAS software version 9.3 using PROC POWER, Twosamplesurvival test = logrank.

The total sample size of 288 represents the approximate number of subjects that may be necessary for 255 PFS events to occur within the projected 36 months of the trial. If a 10% inflation factor is applied to this total (about 29 subjects) to take into account those subjects that may be lost to follow-up prior to documented progression, a total of 317 enrolled subjects may be necessary in order to observe 255 PFS events.

The observed rates of PFS events, recruitment, and drop-outs will be monitored throughout the study and may be used to alter the number of sites, the accrual period, and the follow-up period to achieve the required 255 PFS events in a timely manner. If the 255 PFS events are not observed within 36 months from the start of enrollment the study will be stopped at approximately 24 months after the last randomized subject's first dose.

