6.11.2 Efficacy Analysis Methodology

6.11.2.1 Analysis of Primary Efficacy Variable

The primary comparison of progression-free survival between KW-0761 and vorinostat will be performed on the ITT set based upon the results of the on-site Investigator's assessment using a stratified Log-rank test at the one-sided 2.5% significance level. Stratification is done by disease type (MF or SS), disease stage (IB/II or III/ IV), and region (U.S., Japan, and Rest of World). A Cox proportional hazard model with treatment, disease type, disease stage, and region (U.S., Japan, and Rest of World) as covariates will be used to assess the magnitude of the treatment difference in PFS. The hazard ratio along with the 95% confidence interval obtained from the Cox proportional hazard model will be presented. Additional analyses may be performed adjusting for treatment and other baseline characteristics.

The median PFS and the 2-sided 95% confidence interval for each treatment will be estimated using the Kaplan-Meier survival analysis methods. Kaplan-Meier estimate of PFS rates and the corresponding 95% confidence interval will also be provided for each treatment arm by 6 months intervals. Plots of the Kaplan-Meier estimate of the survival distribution function over time for PFS will be presented by treatment arm.

The primary analysis of PFS will be performed when 255 total PFS events have been observed or 24 months after the last randomized subject's first dose, whichever comes first.

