The following tables will have similar layouts as Tables 14.2.2.1.1, 14.2.2.1.3, 14.2.2.1.4, 14.2.2.1.5 except the p-values will be removed.

Table 14.2.2.3.1
Summary of Confirmed Overall Response Rate (ORR) During Randomized Treatment Period
Efficacy Evaluable Set

Table 14.2.2.3.2
Summary of Confirmed and Unconfirmed Overall Response Rate (ORR) During Randomized Treatment Period
Efficacy Evaluable Set

Table 14.2.2.3.3
Summary of Confirmed Overall Response Rate (ORR) During Randomized Treatment Period by Disease Type
Efficacy Evaluable Set

Table 14.2.2.3
Summary of Confirmed and Unconfirmed Overall Response Rate (ORR) During Randomized Treatment Period by Disease Type
Efficacy Evaluable Set

The following tables will have similar layout as Tables 14.2.2.2.1 and 14.2.2.2.2.

Table 14.2.2.4.1
Summary of Best Overall Response During Randomized Treatment Period
Efficacy Evaluable Set

Table 14.2.2.4.2
Summary of Best Overall Response During Randomized Treatment Period by Disease Type
Efficacy Evaluable Set

Table 14.2.2.5
 Summary of Overall Response During Randomized Treatment Period by Selected Time Points
 Investigator's Assessment
 Intent-to-Treat Set

Overall Response	Vorinostat N=xxx		KW-0761 N=xxx	
	n	(%)	n	(%)
End of Cycle 3				
Complete response (CR)	xx	(xx.x)	xx	(xx.x)
Partial response (PR)	xx	(xx.x)	xx	(xx.x)
Stable disease	xx	(xx.x)	xx	(xx.x)
Progressive disease	xx	(xx.x)	xx	(xx.x)
Not Assessable*	xx	(xx.x)	xx	(xx.x)
End of Cycle 5				
Complete response (CR)	xx	(xx.x)	xx	(xx.x)
Partial response (PR)	xx	(xx.x)	xx	(xx.x)
Stable disease	xx	(xx.x)	xx	(xx.x)
Progressive disease	xx	(xx.x)	xx	(xx.x)
Not Assessable*	xx	(xx.x)	xx	(xx.x)

Note: Percentage is calculated using the number of subjects in the column heading as the denominator.

* If there is no post-baseline tumor assessment or the response for all post-baseline tumor assessments is not assessable or unable to evaluate, the best overall response is classified as not assessable.

<< Programming Note: Repeat for Cycles 7, 11, 13, 25).>>

Table 14.2.2.6.1
 Summary of Duration of Response During Randomized Treatment Period
 Intent-to-Treat Set

	Vorinostat N=xxx	KW-0761 N=xxx
By Investigator's Assessment		
Number of Subjects with Confirmed CR or PR	N'=xx	N'=xx
Subjects with Progressive Disease (n, %)	xx (xx.x)	xx (xx.x)
Subjects Censored (n, %)	xx (xx.x)	xx (xx.x)
Duration of Response (months)		
Kaplan-Meier Estimate		
Q1	xx.x	xx.x
Median (95% CI)*	xx.x (xx.x, xx.x)	xx.x (xx.x, xx.x)
Q3	xx.x	xx.x

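### SAP Table 14.2.2.5 divides Cycle 25 responses by all ITT subjects, although on the planned inputs about 42–48% could not yet have had that visit at the data cutoff

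*SAP*

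**What the plan says.** Table 14.2.2.5 (SAP mock-up tables; ITT Set, investigator's assessment) gives counts and percentages of CR, PR, SD, PD and Not Assessable at the end of Cycles 3 and 5. The programming note extends it: "Programming Note: Repeat for Cycles 7, 11, 13, 25". The only denominator rule is: "Note: Percentage is calculated using the number of subjects in the column heading as the denominator".

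The timing follows from other sections:

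- SAP 3.2.2.1: "Each treatment cycle is 28 days". Cycle 25 therefore ends on day 25 × 28 = 700.
- SAP 5.1: after year 1, "the overall global composite response will be documented every 16 weeks (Cycle 17, 21, etc". Cycle 25 is the next visit in that series, so it is a scheduled global assessment.
- SAP 6.11.2.1: "The primary analysis of PFS will be performed when 255 total PFS events have been observed". A fallback applies if it comes sooner: two years from the date on which the subject randomized last was first dosed.
- SAP 6.3: "For a 24-month accrual and 12 month follow-up on the last subject dosed", with 255 events expected within 36 months.

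The table's Not Assessable footnote is worded for best overall response across all post-baseline assessments. It does not say where to count a subject whose Cycle 25 visit is still in the future.

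**The concern.** A subject randomized less than 700 days before the cutoff cannot have a Cycle 25 assessment, however well the disease is controlled. The shell keeps that subject in the denominator, where the subject can never be a CR or PR. An ongoing responder who is not yet due lowers the percentage exactly as a subject who has progressed does.

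Kaplan-Meier estimation deals with short follow-up for PFS and DOR. This table is a raw proportion and has nothing equivalent. A reader comparing the Cycle 13 and Cycle 25 rows would see more loss of response than occurred, with the excess due to enrollment dates alone.

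**Working it through.** **Inputs.** Medians of 169 and 254 days, one-sided 0.025, 90% power, 255 events, 24-month accrual, 36 months in total, N = 288 and then 317 after 10% inflation (SAP 6.3); 1:1 allocation (SAP 3.2.1). Assumed here: exponential PFS, uniform accrual, loss unrelated to arm, treatment starting at randomization, and a month of 30.4375 days, so accrual A = 730.5 days.

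**1. Reproduce the plan.** The hazard ratio is 169/254 = 0.665. Schoenfeld's formula gives 254 events for 90% power, and 255 events give 90.2%. With λ = ln 2/median, the chance of an event by calendar time T is, per arm, 1 − [exp(−λ(T − A)) − exp(−λT)]/(λA). At T = 36 months this is 0.929 for vorinostat and 0.840 for KW-0761, averaging 0.8846. Then 255/0.8846 = 288.3, and 288 × 1.10 = 317. The plan's figures are recovered.

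**2. Date of event 255 and share not yet due.** Solve expected events = 255 for T. The share not due at cycle c is 1 − (T − 28c)/730.5, limited to between 0 and 1.

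| Scenario (24-month accrual) | Cutoff, months | Not due, Cycle 25 | Not due, Cycle 13 | N' at Cycle 25 |
|---|---|---|---|---|
| 317, 10% lost at a constant rate | 35.4 | 48% | 2% | 164 |
| 317, 10% never yield an event | 36.9 | 42% | 0% | 183 |
| 288, no loss | 36.1 | 46% | 0% | 157 |
| 317, 5% lost | 32.4 | 61% | 15% | 124 |
| 317, no loss | 30.6 | 68% | 23% | 100 |
| 317, 15% lost | 42.2 | 20% | 0% | 254 |
| 24-month fallback trigger | 48.0 | 0% | 0% | 317 |

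Example for row 1: T = 1078 days, and 1 − (1078 − 700)/730.5 = 0.48. A 3,000-trial simulation of row 2 gave a mean of 42% not due (5th to 95th percentile 23–58%). At Cycle 11 the share is 0% with 10% loss and 15% with none. At Cycle 7 it is 0% throughout. With accrual stretched to 30–40 months, the Cycle 25 share is 36–61% across the no-loss and 10%-loss cases.

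**3. Effect on the printed rate.** Entry date does not depend on outcome or arm, so the printed rate is the rate among subjects with enough follow-up × (1 − share not due). With 10% loss that multiplier is 0.52 to 0.58.

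**4. Size in percentage points.** A subject in response must be progression-free, so planned PFS at day 700 is a ceiling on the response rate:

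- KW-0761: 2^(−700/254) = 14.8%, printed as 14.8 × 0.52 to 0.58 = 7.7–8.6%.
- Vorinostat: 2^(−700/169) = 5.7%, printed as 5.7 × 0.52 to 0.58 = 3.0–3.3%.

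The simulation gave 8.8% and 3.4%. The shortfall is therefore at most about 7 points for KW-0761 (14.8 − 7.7 = 7.1) and 3 points for vorinostat (5.7 − 3.0 = 2.7).

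**The case against.** The strongest reply is that this is one row of a descriptive table. The shell prints no arm difference, confidence interval or p-value, and durability is reported properly by Kaplan-Meier. All of that stands, and it limits the importance of the point.

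Second, the SAP has rules that might seem to cover the case. SAP 8.1.5 calls for an Unknown or Missing category where information is lacking. That would make the affected subjects visible, but it would mix visits not yet due with dropout and leave the percentage unchanged. SAP 6.11.1.2.1 counts ITT subjects without valid data as nonresponders, but for confirmed ORR over the treatment period, not for a fixed late visit. The general default in SAP 8.1.5, subjects with an observation, gives way to the table's own note. It would also overcorrect here, because it drops subjects who had already progressed.

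Third, a fall from Cycle 13 to Cycle 25 is expected anyway: planned PFS goes from 37.0% to 14.8% for KW-0761 and from 22.5% to 5.7% for vorinostat. This is true. The denominator adds to a real decline and does not create it.

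A reader might also infer that these subjects can never be assessed at Cycle 25 on the protocol schedule. Protocol 7.7 does not establish this: efficacy data continue for a year after the primary analysis, and the move to local standard of care waits for the Sponsor's notification.

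**Conclusion.** The point holds for the Cycle 25 row. On the planned inputs with 10% loss, about 42–48% of ITT subjects could not have reached that visit at the 255-event cutoff, and the printed rates would be about 0.52–0.58 of those among subjects with enough follow-up. This rests on exponential PFS, uniform 24-month accrual and loss unrelated to arm.

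A reader might infer that half or more of the subjects are affected, that late response rates are distorted generally, or that the treatment comparison is biased. The documents do not support these readings. A share above one half needs less loss than the 10% that justifies enrolling 317. It falls to 20% at 15% loss and to zero under the fallback trigger. At 10% loss, Cycle 13 is affected by at most about 2% and earlier cycles not at all; the 23% at Cycle 13 arises only with no loss. Both arms shrink by the same factor, so their ratio is unchanged, and a difference that a reader computes by hand shrinks by that factor too. ORR, PFS and DOR are unaffected.

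**What to change.** In Table 14.2.2.5, replace the column N at each time point by N': the ITT subjects whose start date plus 28 × cycle days, plus the visit window, is on or before the data cutoff. Decide this by calendar date alone, regardless of outcome. Print N' per arm and time point, and show the remaining subjects in a row such as *visit not yet due at cutoff*.

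Keep eligible subjects who progressed, died, crossed over or dropped out in N' as not in response. Treat subjects who stopped treatment after a CR differently. SAP 3.2.2.3 limits treatment after an overall CR to 12 months, and SAP 5.6 then schedules response assessments off treatment. Classify these subjects by those follow-up assessments, stating which assessment is matched to the time point, or show them in a separate row. They should not be counted as nonresponders by default.

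The cost is one derived flag, one footnote and one or two extra rows. The Cycle 25 percentages would rest on about 160–185 subjects in total on the planned inputs and so be less precise. If the 24-month fallback triggers the analysis, N' returns to the full ITT set.

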6.11.2.5 Analyses of Exploratory Efficacy Variables

Although not considered a secondary endpoint, a comparison between treatment arms for OS and TTF will be conducted using the same method as described above for the analysis of PFS based on the ITT set and will be considered exploratory.

Additional exploratory analysis will be performed for comparison of PFS between subjects with any exposure to KW-0761 versus subjects with vorinostat only. For this analysis, the PFS for subjects who cross over from the vorinostat arm to KW-0761 will be calculated from the first dose of KW-0761.

Statistical analyses on OS using follow-up data may take place after database lock for the study and will be reported as supplemental to the Clinical Study Report.

The following exploratory analyses will be performed for OS to account for crossover effect:

- The rank-preserving structural failure time (RPSFT) model will be applied to allow a direct comparison of the randomized treatment groups by adjusting the OS of subjects who crossed over so that it reflects the OS had they not received KW-0761.¹²
- The Inverse Probability of Censoring Weighting (IPCW) model will also be applied. In this method subjects who cross over from IC to KW-0761 will be censored and subjects remaining on IC will be weighted to compensate for missing data. The bias introduced by the crossover will be corrected by weighting each subject by the inverse of the predicted probability of not being censored at a given time.¹²

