8.2.5 SAS[®] Procedures

This section provides sample SAS[®] code to illustrate statistical tests specified in the statistical methods section. All computer output from SAS[®] statistical procedures serving as a basis for extracted results (e.g., LIFETEST) will be retained for quality control procedures and will be included in CSR appendices.

- 1) Stratified Log Rank test for PFS between treatment:

```
proc lifetest method=KM;
    time PFS*censor(1);
    strata type stage region/group=trt;
run;
```
- 2) Hazard ratio from Cox proportional hazard model for PFS:

```
proc phreg;
    model PFS*censor(1)=trt type stage region/risklimits ties=efron;
run;
```
- 3) CMH test for ORR between treatment:

```
proc freq;
    tables type*stage*region*trt*resp/cmh;
run;
```
- 4) Exact 95% confidence interval on ORR and exact 95% unconditional confidence interval for the risk difference:

```
proc freq;
    tables trt*resp;
    exact riskdiff;
run;
```
- 5) ANCOVA for change in QoL score between treatment:

```
proc mixed;
    class trt type stage region timept usubjid;
    model QoL_chng = trt type stage region base_QoL timept
        trt*timept/solution;
    repeated timept / subject=usubjid type=un;
    lsmeans trt/pdiff cl;
run;
```
- 6) Wilcoxon Rank Sum test for change in Likert Scale score between treatment:

```
proc npar1way wilcoxon hl;
    class trt;
    var QoL_chng;
run;
```

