Hazard Ratio (95% CI)**		xx.x (xx.x, xx.x)
p-value**		x.xxxx

Note: Percentage is calculated using the number of subjects in the column heading as the denominator. RPSFT = rank-preserving structural failure time.

* 95% CIs are obtained from SAS proc lifetest using loglog transformation.

** Hazard ratio, 95% CIs and p-value are obtained from RPSFT model.

Table 14.2.9.3
 Overall Survival (OS) Analysis Using IPCW Model
 Intent-to-Treat Set

	Vorinostat N=xxx	KW-0761 N=xxx
Subjects Died (n, %)	xx (xx.x)	xx (xx.x)
Subjects Censored (n, %)	xx (xx.x)	xx (xx.x)
Overall Survival (months)		
Kaplan-Meier Estimate of OS		
Q1	xx.x	xx.x
Median (95% CI)*	xx.x (xx.x, xx.x)	xx.x (xx.x, xx.x)
Q3	xx.x	xx.x
Mean	xx.xx	xx.xx
Standard Deviation	xx.xxx	xx.xxx
Median	xx.xx	xx.xx
Minimum	xx.x	xx.x
Maximum	xx.x	xx.x
----- Treatment Comparison -----		
KW-0761 vs. Vorinostat		
Hazard Ratio (95% CI)**		xx.x (xx.x, xx.x)
p-value**		x.xxxx

Note: Percentage is calculated using the number of subjects in the column heading as the denominator. IPCW = inverse probability of censoring weighting.

* 95% CIs are obtained from SAS proc lifetest using loglog transformation.

** Hazard ratio, 95% CIs and p-value are obtained from the IPCW model.

Table 14.2.10
 Summary of Time to Treatment Failure (TTF)
 Intent-to-Treat Set

	Vorinostat N=xxx	KW-0761 N=xxx
Subjects with Treatment Failure (n, %)	xx (xx.x)	xx (xx.x)
Earliest Contributing Events:		
Discontinuation of Randomized Treatment Due to	xx (xx.x)	xx (xx.x)
PD per CTCL response criteria	xx (xx.x)	xx (xx.x)
Clinical progression	xx (xx.x)	xx (xx.x)
Adverse event	xx (xx.x)	xx (xx.x)
Death	xx (xx.x)	xx (xx.x)
Initiation of Another New Anti-cancer Therapy	xx (xx.x)	xx (xx.x)
Subjects Censored (n, %)	xx (xx.x)	xx (xx.x)
Time to Treatment Failure (months)		
Kaplan-Meier Estimate of TTF		
Q1	xx.x	xx.x
Median (95% CI)*	xx.x (xx.x, xx.x)	xx.x (xx.x, xx.x)
Q3	xx.x	xx.x
Mean	xx.xx	xx.xx
Standard Deviation	xx.xxx	xx.xxx
Median	xx.xx	xx.xx
Minimum	xx.x	xx.x
Maximum	xx.x	xx.x
----- Treatment Comparison -----		
KW-0761 vs. Vorinostat		
Hazard Ratio (95% CI)**		xx.x (xx.x, xx.x)
Log rank p-value*		x.xxxx
Rate (%) of Being Alive without Treatment Failure for at Least***		
6 months (95% CI)	xx.x (xx.x, xx.x)	xx.x (xx.x, xx.x)
12 months (95% CI)	xx.x (xx.x, xx.x)	xx.x (xx.x, xx.x)
18 months (95% CI)	xx.x (xx.x, xx.x)	xx.x (xx.x, xx.x)
24 months (95% CI)	xx.x (xx.x, xx.x)	xx.x (xx.x, xx.x)
Etc.		

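### The LIFETEST interval for the vorinostat median in the RPSFT survival table omits the uncertainty in the acceleration factor; the SAP leaves the other crossover-adjusted intervals, and the weighting of the IPCW medians, undefined

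*SAP*

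**What the plan says.** SAP Section 6.11.2.5 adds two exploratory OS analyses to account for crossover.

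- **RPSFT.** The randomized arms are compared "by adjusting the OS of subjects who crossed over so that it reflects the OS had they not received KW-0761".
- **IPCW.** "In this method subjects who cross over from IC to KW-0761 will be censored", and the remedy is "weighting each subject by the inverse of the predicted probability of not being censored at a given time". (IC is not defined in the SAP; the comparator is vorinostat.)

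The shells for Tables 14.2.9.2 (RPSFT) and 14.2.9.3 (IPCW) each have a Kaplan-Meier block with a median and its interval. The single-asterisk footnote on that interval is identical in both, and identical to the one in the unadjusted OS Table 14.2.9.1: "95% CIs are obtained from SAS proc lifetest using loglog transformation". The double-asterisk footnotes read "Hazard ratio, 95% CIs and p-value are obtained from RPSFT model" and "Hazard ratio, 95% CIs and p-value are obtained from the IPCW model".

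The only LIFETEST sample code, in SAP Section 8.2.5, is written for PFS. It opens with "proc lifetest method=KM" and has no weight statement. Neither the protocol nor the SAP says how the acceleration factor is estimated, whether adjusted times are recensored, how the RPSFT hazard ratio, interval and p-value are built, what variance IPCW uses, or whether the Kaplan-Meier rows of Table 14.2.9.3 are weighted.

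**The concern.** A footnote that is correct for observed survival times has been carried over to times that are not observed.

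In the RPSFT table a crossover subject's vorinostat time is constructed by shrinking or stretching the time on KW-0761 by an estimated factor. That factor varies from sample to sample and moves the whole adjusted curve. LIFETEST sees only the constructed times, so its interval reflects the number of deaths and censorings and none of the error in the factor.

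The other two parts are gaps. An RPSFT model estimates an acceleration factor; a hazard ratio needs a second step, and that step is not described. In the IPCW table the Kaplan-Meier rows could be produced with or without weights. Without them, the printed curve would be the one censored at crossover, whose bias Section 6.11.2.5 says the weights are there to remove, beside a weighted hazard ratio.

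Crossover is allowed at progression or for intolerance (Protocol Sections 3.4 and 5.3) and stays open for up to a year after the primary data cutoff (Section 7.7). The adjustment could therefore be large, and a reader of these tables could take the adjusted survival difference as more certain than it is.

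**Working it through.** The documents give no OS rate, crossover share, acceleration factor or weight model, so there is no plan figure to reproduce. The calculations below are illustrations. From the documents they take 317 subjects, 1:1 allocation and a vorinostat median PFS of 169 days (169 / 30.4375 = 5.55 months), used as the time to possible crossover. Everything else is assumed.

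**1. RPSFT median interval.** Assumptions: exponential OS with a 24-month median on vorinostat alone, true hazard ratio 0.75, censoring uniform over 12 to 36 months, a crossover share p, and 600 simulated trials per share.

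- Counterfactual time: U = (time off KW-0761) + exp(ψ) × (time on KW-0761), recensored at min(C, C·exp(ψ)).
- ψ is chosen so that the log-rank statistic between arms on U is as close to zero as possible.
- The log-log interval covers the true median m when |ln(−ln Ŝ(m)) − ln(ln 2)| ≤ 1.96 × √V / |ln Ŝ(m)|, with V the Greenwood sum.

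Coverage for the vorinostat column, nominal 95%:

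| Crossover | 50% | 70% | 90% |
|---|---|---|---|
| LIFETEST-type interval | 90% | 83% | 76% |

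Recensoring ends the adjusted follow-up before 24 months in some trials; scoring those intervals as open above hardly changes the result. With ψ held at its true value the same interval is close to nominal, so the loss comes mainly from estimating ψ. A 36-month OS median was also run, but its Kaplan-Meier coverage is not used because that median lies at the end of follow-up.

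**2. RPSFT hazard ratio, if it came from an ordinary Cox model on adjusted times.** Same simulation, coverage of the 95% interval:

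| Crossover | 50% | 70% | 90% |
|---|---|---|---|
| Cox, ψ treated as known, OS median 24 months | 84% | 75% | 66% |
| Cox, ψ treated as known, OS median 36 months | 87% | 81% | 68% |

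The mean Cox standard error was 0.19 to 0.23 against a true SD of the log hazard ratio of 0.27 to 0.46. Inverting the g-estimation test covered 93% to 95%, and an interval that keeps the ITT p-value covered 91% to 93%.

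For the p-value: at ψ = 0 the g-estimation test is the ITT log-rank test, so RPSFT carries no evidence against the null beyond ITT. In 600 null trials per share (assumed mean survival 80 months before and 21 months after progression), the Cox test on adjusted times was nominally significant in 18%, 26% and 40% of trials at 50%, 70% and 90% crossover, against 4% to 5% for ITT.

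**3. IPCW median, if the Kaplan-Meier rows were unweighted.** Let λ = ln 2 / 5.55 per month (progression), h0 = 0.005 per month (death before progression, assumed) and h1 = ln 2 / (post-progression median). A share p crosses over at progression.

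- Alive, not progressed: A(t) = exp(−(λ + h0)t).
- Alive, progressed: B(t) = λ / (λ + h0 − h1) × [exp(−h1·t) − exp(−(λ + h0)t)].
- Survival without crossover, the target of correct weighting: A + B.
- Hazard seen by an unweighted curve censored at crossover: [A·h0 + (1 − p)·B·h1] / [A + (1 − p)·B].

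Vorinostat median in months, with the excess in brackets:

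| Post-progression median | Weighted (true) | Unweighted, p = 50% | p = 70% | p = 90% |
|---|---|---|---|---|
| 12 | 19.6 | 22.8 (+3.2) | 25.7 (+6.1) | 33.4 (+13.8) |
| 24 | 31.1 | 33.9 (+2.8) | 36.4 (+5.3) | 42.7 (+11.6) |
| 36 | 42.2 | 44.7 (+2.5) | 46.8 (+4.6) | 52.3 (+10.1) |

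**The case against.** The strongest reply is that only one of the three parts rests on stated text.

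A reader might infer that the RPSFT hazard ratio interval also ignores the acceleration factor. The footnote does not say so. It attributes the result to the RPSFT model, whereas Table 14.2.9.1 names a Cox model and a stratified log-rank test. A model-based interval can come from inverting the g-estimation test, which carries the uncertainty. The Cox figures above therefore describe one possible implementation.

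A reader might also infer that the IPCW medians drop the weights. The footnote describes the interval and is silent on the estimator; Section 6.11.2.5 says that each subject is weighted; and the unweighted LIFETEST code is for PFS. The documents support only that the shell leaves it unclear.

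Both methods cite a paper on OS under crossover that is not available here and may describe the intervals. OS is exploratory, outside the primary test and the four Sidak-adjusted tests, and the ITT analysis has its own table with a log-rank p-value. LIFETEST intervals are also ordinary for the KW-0761 column where its times are observed and unweighted.

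All of this stands, and it limits the second and third parts to gaps in specification. It does not answer the first: the interval for the RPSFT median is expressly assigned to LIFETEST, and for vorinostat that leaves out the error in the factor.

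**Conclusion.** The point holds in a limited form. In Table 14.2.9.2 the stated rule makes the vorinostat median interval too narrow, with illustrative coverage of about 90%, 83% and 76% at 50%, 70% and 90% crossover. How the RPSFT hazard ratio, interval and p-value are obtained is unspecified; an ordinary Cox model on adjusted times would understate the uncertainty. Whether the IPCW Kaplan-Meier rows are weighted is also unspecified; if they are not, the vorinostat median is too long, by about 2.5 to 14 months in the scenarios tried.

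The documents do not support saying that the SAP prescribes a test that declares noise significant, or that these tables will carry the survival message. The primary result and the multiplicity-controlled tests are unaffected. The sizes depend on assumed OS, crossover and follow-up; the direction of the RPSFT median problem does not depend on the particular values chosen.

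**What to change.** **Table 14.2.9.2.** For the vorinostat column, replace the LIFETEST footnote with a bootstrap interval that re-estimates the acceleration factor in each resample. Take the hazard ratio interval from the same bootstrap or from test inversion, and print the ITT log-rank p-value from Table 14.2.9.1. State in Section 6.11.2.5 how the factor is estimated and whether recensoring is applied.

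**Table 14.2.9.3.** State that the vorinostat Kaplan-Meier estimate is weighted, and take the intervals for the median and hazard ratio from a bootstrap that refits the weight model. Replace the undefined IC with vorinostat in the text.

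In both tables LIFETEST intervals may stay for the KW-0761 column where its times are observed and unweighted.

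The cost is a few lines of SAP and shell text, some bootstrap programming, and wider reported intervals. No extra data are needed.
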